1.2 Secondary Endpoint(s)

1.2.1 Assess secondary clinical endpoints such as the percent of patients receiving neoadjuvant cetuximab who progress by CT RECIST 1.1 criteria during the neoadjuvant cetuximab. All patients in the protocol will receive a CT with IV contrast prior and also after neoadjuvant cetuximab. Progression will be gauged using the RECIST 1.1 CT criteria for progression (at least a 20% increase in the sum of the LD of target lesions, taking as reference the pre-cetuximab scan or the appearance of one or more new lesions). If it is found that the prior probability that 20% or more of the patients are progressing during neoadjuvant cetuximab is at least 90%, the protocol will be stopped (section 16.8). The first interim analysis will be performed after 12 patients. We will also assess the 2 yr locoregional control for non-responders to neoadjuvant cetuximab. We will also assess the complete response rate to PET/CT scan 3 months after the completion of radiation therapy for both responders and for

non-responders to neoadjuvant cetuximab, as PET/CT has a NPV of 95% in this setting, so will give a very good indication of eventual locoregional control.³

1.2.2 Molecular correlates. All patients must have a biopsy of the locoregional disease (primary site or neck lymph nodes), and of the skin prior to therapy. When feasible, patients will also have another biopsy of the locoregional disease and skin after 3 weeks of neoadjuvant cetuximab but prior to starting radiation therapy. If there is a locoregional recurrence, a third biopsy of locoregional disease is possible. The second biopsy after neoadjuvant cetuximab and third biopsy in case of recurrence are strongly recommended but not absolutely necessary for participation in the protocol. Therefore, this protocol offers a unique chance to investigate molecular correlates because 1) the neoadjuvant therapy is a single agent, as opposed to a chemotherapy cocktail (and so the change in protein production is due to a single agent as well), 2) we will obtain normal tissue (skin) samples and tumor samples from before and after 3 weeks of cetuximab, so we will have in-vivo tissue to analyze after this single agent.

Our goals in the molecular analysis are to explore the following possibilities:

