7.2.3.2 CT response by RECIST 1.1 criteria

The week after the 3rd dose of neoadjuvant cetuximab (Day 14-21 after the first dose of cetuximab), the patient will have a CT neck with IV contrast for comparison to the first CT neck performed prior to neoadjuvant cetuximab. CT response will be evaluated using RECIST 1.1 criteria: (E.A. Eisenhauer et al. New response evaluation criteria in solid tumours: Revised RECIST guideline (version 1.1). EUR J CANCER 45 (2009) 228-247].

Evaluation of Target Lesions

| | |
|---------------------------|---|
| Complete Response (CR): | Disappearance of all target lesions. Any pathological lymph nodes (whether target or non-target) must have reduction in short axis to <10 mm. |
| Partial Response (PR): | At least a 30% decrease in the sum of diameters of target lesions, taking as reference the baseline sum diameters. |
| Progressive Disease (PD): | At least a 20% increase in the sum of diameters of target lesions, taking as reference the smallest sum on study (this includes the baseline sum if that is the smallest on study). In addition to the relative increase of 20%, the sum must also demonstrate an absolute increase of at least 5 mm. (Note: the appearance of one or more new lesions is also considered progression). |
| Stable Disease (SD): | Neither sufficient shrinkage to qualify for PR nor sufficient increase to qualify for PD, taking as reference the smallest sum diameters while on study |

Please note that significant changes from version 1.0 include for malignant lymph nodes: To be considered pathologically enlarged and measurable, a lymph node must be >15mm in short axis when assessed by CT scan (CT scan slice thickness recommended to be no greater than 5 mm). At baseline and in follow-up, only the short axis will be measured and followed.

7.2.4 Repeat Bx after neoadjuvant cetuximab. After 3 weeks of neoadjuvant cetuximab, a biopsy specimen (incisional/core biopsy as opposed to a FNA) will be procured from the head and neck primary site). As this tissue will be used for DNA and RNA sequencing, tissue that is preserved and sufficient in quantity is required. These specimens will be handled as delineated in 11.3.

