8.4 Definition of Unexpected

Any adverse drug experience and/or specificity, that is not included in the current investigator's brochure and/or package insert.

9. Treatment Evaluation/Criteria for Response

For the purposes of this study, the response to neoadjuvant cetuximab is judged by 1) development of cetuximab related folliculitis as below and 2) response at the primary site and neck by CT using RECIST 1.1 criteria.

Response and progression will be evaluated in this study using the international criteria proposed by the Response Evaluation Criteria in Solid Tumors (RECIST 1.1) Committee [JNCI 92(3): 205-216, 2000]. Changes in only the largest diameter (unidimensional measurement) of the tumor lesions are used in the RECIST 1.1 criteria. Note: Lesions are either measurable or non-measurable using the criteria provided below. The term "evaluable" in reference to measurability will not be used because it does not provide additional meaning or accuracy.

In addition, patients will be evaluated weekly during neoadjuvant cetuximab to assess for grade of rash using CTCAE 4.0 criteria.

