9.2 Evaluation of CT response at primary site and neck

CT scans of the neck with IV contrast will be taken before and after neoadjuvant cetuximab (Day 14-21 after the first dose of cetuximab). At the primary site and neck lymph nodes, the largest diameter on axial CT slices will be measured and recorded. All measurements will be taken and recorded in metric notation using measuring software in the applicable radiology programs. In all possible cases, spiral CT (as opposed to standard CT) will be performed. Response will be graded per RECIST 1.1 criteria: [E.A. Eisenhauer et al. New response evaluation criteria in solid tumours: Revised RECIST 1.1 guideline (version 1.1). Eur J Cancer 45 (2009) 228-247].

Evaluation of Target Lesions

| | |
|---------------------------|---|
| Complete Response (CR): | Disappearance of all target lesions. Any pathological lymph nodes (whether target or non-target) must have reduction in short axis to <10 mm. |
| Partial Response (PR): | At least a 30% decrease in the sum of diameters of target lesions, taking as reference the baseline sum diameters. |
| Progressive Disease (PD): | At least a 20% increase in the sum of diameters of target lesions, taking as reference the smallest sum on study (this includes the baseline sum if that is the smallest on study). In addition to the relative increase of 20%, the sum must also demonstrate an absolute increase of at least 5 mm. (Note: the appearance of one or more new lesions is also considered progression). |
| Stable Disease (SD): | Neither sufficient shrinkage to qualify for PR nor sufficient increase to qualify for PD, taking as reference the smallest sum diameters while on study |

Please note that significant changes from version 1.0 include for malignant lymph nodes: To be considered pathologically enlarged and measurable, a lymph node must be >15mm in short axis when assessed by CT scan (CT scan slice thickness recommended to be no greater than 5 mm). At baseline and in follow-up, only the short axis will be measured and followed.

10. Removal of Patients from Study/Off Study Criteria

In the absence of treatment delays due to adverse events, treatment may continue until one of the following criteria applies:

- a) Intercurrent illness that prevents further administration of treatment,
- b) Patient decides to withdraw from the study,
- c) Noncompliance with treatment plan,

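### Section 9.2 gives two incompatible rules for measuring neck nodes; short axis is clearly intended, but the leftover largest-diameter wording in 9.2, 9 and 1.2.1 could change a CT call and should be corrected

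*Combined protocol and SAP*

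**What the plan says.** Section 9.2 begins: "At the primary site and neck lymph nodes, the largest diameter on axial CT slices will be measured and recorded". It then says "Response will be graded per RECIST 1.1 criteria" and cites the 2009 guideline. Its closing note on malignant lymph nodes says: "At baseline and in follow-up, only the short axis will be measured and followed".

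Section 7.2.3.2 carries the same nodal note, introduced by "Please note that significant changes from version 1.0 include for malignant lymph nodes", and the same 2009 citation. It has no largest-diameter sentence. Its progression definition adds: "In addition to the relative increase of 20%, the sum must also demonstrate an absolute increase of at least 5 mm". For non-nodal lesions it refers only to a sum of diameters and does not say which diameter.

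The introduction to section 9 says: "Changes in only the largest diameter (unidimensional measurement) of the tumor lesions are used in the RECIST 1.1 criteria". It names as its source the "Response Evaluation Criteria in Solid Tumors (RECIST 1.1) Committee [JNCI 92(3): 205-216, 2000".

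Section 1.2.1 invokes the RECIST 1.1 criteria for progression and explains them in parentheses as "at least a 20% increase in the sum of the LD of target lesions, taking as reference the pre-cetuximab scan", or a new lesion. LD is not in the abbreviation list; longest diameter is the natural reading.

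No sentence says which of these prevails.

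**The concern.** Within 9.2 the two instructions both name nodes and both govern measurement, so they cannot both be obeyed. Sections 9 and 1.2.1 add to the confusion by stating an all-lesion rule without excepting nodes.

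The CT category has three uses in this trial:

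- **Treatment.** Under 7.2.5, CT progression sends the patient to cisplatin RT whatever the skin shows. Stable disease with folliculitis, or a partial response, leads to cetuximab RT. This also decides who enters the responder cohort in which the primary endpoint, 2-year locoregional control, is measured.
- **Endpoint.** The percentage progressing during neoadjuvant cetuximab is a reported secondary outcome (1.2.1, 16.4, 16.5).
- **Stopping.** Section 16.8 stops the trial on the number of progressions, first at 12 patients and then after each further patient.

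**Working it through.** **Step 1. The texts side by side.**

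| Place | Names nodes? | Diameter | Source cited |
|---|---|---|---|
| 9.2, opening | yes | largest | 2009 guideline, for grading |
| 9.2, closing note | yes | short axis only | same section |
| 9.2 and 7.2.3.2, complete response | yes | short axis, below 10 mm | 2009 guideline |
| 9.2 and 7.2.3.2, measurability | yes | short axis, above 15 mm | 2009 guideline |
| 7.2.3.2, nodal note | yes | short axis only | 2009 guideline |
| 9, introduction | no | largest, all tumor lesions | 2000 publication |
| 1.2.1, parenthetical | no | LD, all target lesions | RECIST 1.1 by name only |

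The node-against-node contradiction is between the first two rows. Sections 9 and 1.2.1 conflict only by omitting a nodal exception.

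**Step 2. Can the choice change a category?** The thresholds come from 7.2.3.2 and 9.2: partial response at -30%; progression at +20% and at least 5 mm. The lesion sizes are assumed for illustration: one primary and one node, in mm, with each node above 15 mm in short axis at baseline.

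| Case | Primary | Node (long x short) | Sum with largest diameter | Sum with nodal short axis |
|---|---|---|---|---|
| (a) | 30 to 33 | 30x18 to 41x20 | 60 to 74: 74/60 = 1.233, +23.3%, progression | 48 to 53: 53/48 = 1.104, +10.4%, stable |
| (b) | 30 to 33 | 30x18 to 32x27 | 60 to 65: 65/60 = 1.083, +8.3%, stable | 48 to 60: 60/48 = 1.250, +25.0%, progression |
| (c) | 30 to 22 | 30x20 to 18x16 | 60 to 40: 40/60 = 0.667, -33.3%, partial response | 50 to 38: 38/50 = 0.760, -24.0%, stable |

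A 1 mm shift of a follow-up sum towards the threshold reverses none of these calls:

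- (a) 73/60 = 1.217 and 54/48 = 1.125
- (b) 66/60 = 1.100 and 59/48 = 1.229
- (c) 41/60 = 0.683 and 37/50 = 0.740

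**Step 3. Who is affected?** By the rules in 7.2.5:

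- A switch between stable and progression changes treatment only in folliculitis-positive patients, because folliculitis-negative patients receive cisplatin RT either way. It changes the progression endpoint and the stopping count in any patient.
- A switch between partial response and stable changes treatment only in folliculitis-negative patients. Section 2.1 expects very few of them to qualify by CT.
- A patient with no measurable node has the same sum under both rules. A patient who progresses by a new lesion progresses under both.

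**Step 4. The stopping count.** Section 16.8 uses a Beta(1+k, 1+n-k) posterior and stops when the probability of a progression rate above 20% exceeds 90%. Taking k as the number of progressions, as its worked example does:

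- k = 3, n = 12: P(Beta(4, 10) > 0.20) = 0.747, continue.
- k = 4, n = 12: P(Beta(5, 9) > 0.20) = 0.901, stop.

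Both match the protocol's table, so one reclassified patient can decide the first look.

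**Step 5. The 5 mm minimum missing from 1.2.1.** Since 0.20 x 25 mm = 5 mm, a 20% increase already reaches 5 mm once the baseline sum is 25 mm or more. The omission matters only for smaller sums.

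**The case against.** The strongest reply is that this is a leftover sentence and not an open choice. The nodal note is the more specific text, appears twice, and is presented as a change from version 1.0. It agrees with the complete-response and measurability criteria. Section 9.2 grades by the 2009 guideline immediately after the measuring sentence. Section 7.2.3.2, which feeds the treatment decision, contains no conflicting sentence. Section 1.2.1 offers its LD wording only as a gloss on RECIST 1.1. All of this stands, and it settles the intent. It does not remove the instruction, and the RECIST 1.1 label alone does not guide a reader of this protocol, because section 9 attaches that label to the largest-diameter rule.

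The opening of 9.2 might instead be a recording step, perhaps for the imaging correlates in 1.2.3, which use the longest diameter. The closing note stands against this: if only the short axis of a node is measured, there is no largest nodal diameter to record.

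It is also fair that the examples in (a) and (b) need large, lopsided nodal growth within about three weeks (11 mm against 2 mm, and 2 mm against 9 mm), and that a primary that changes little dilutes the disagreement. The examples show that a category can change, not that it often will.

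A reader might infer that sections 9 and 1.2.1 order the long axis for nodes. They do not mention nodes. A reader might also infer that the stopping rule is materially unreliable. The documents give no discordance rate between the two rules, so any probability of a changed decision would be set by whatever rate was assumed.

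**Conclusion.** The contradiction in 9.2 is real, and the wording in 9 and 1.2.1 supports the wrong side of it by omission. Short axis for nodes is clearly intended. A reader who follows the opening of 9.2 could turn a stable call into progression, the reverse, or a stable call into a partial response. That could change a patient's treatment and cohort, the progression percentage, or a stopping decision (0.747 against 0.901 at 3 and 4 of 12).

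The lesion sizes behind this are assumptions, and the frequency of disagreement cannot be computed from the documents. Patients without a measurable node, and those progressing by a new lesion, are untouched. The missing 5 mm minimum in 1.2.1 is minor.

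The documents do not support reading this as an undecided analysis rule or as a flaw in the design figures: no sample size, power or significance level changes. It is a wrong measuring instruction with a cheap correction, and it should be corrected.

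**What to change.** 1. **7.2.3.2:** add that the sum of diameters uses the longest diameter for the primary (non-nodal) lesion and the short axis for nodes, with progression at +20% and at least 5 mm, or a new lesion. The addition is needed because this section does not now say which diameter applies to the primary. Turning the other passages into cross-references without it would remove the only written rule for the primary.
2. **9.2:** change the opening sentence to match.
3. **9 and 1.2.1:** replace the largest-diameter and LD wording with a reference to 7.2.3.2.
4. **9:** replace the 2000 citation with the 2009 guideline already cited in 7.2.3.2 and 9.2.

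If the longest nodal diameter is wanted for the imaging correlates in 1.2.3, it can be recorded separately and kept out of the sum; this fix does not require it.

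The cost is wording in four places and one citation. The scans and readers stay the same, and no new data field is needed.

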11.2 Tissue to be collected

All patients must have a diagnosis of squamous cell carcinoma (SCC) prior to entering into this protocol, and this diagnosis is typically achieved by a biopsy from either the primary site or FNA from a neck lymph node. However, this protocol requires additional biopsies as the scant amount of tissue obtainable from an FNA would not be adequate for the molecular biology aspect of this protocol, which include

1. Providing a paraffin embedded block which will be sent to FoundationOne™ (or other certified genomic analysis facility) for DNA sequencing and analysis of genetic mutations.
2. Providing frozen tumor to Cancer Institute of New Jersey Functional Genomics Facility for RNA sequencing
3. Providing skin tissue to Cancer Institute of New Jersey Functional Genomics Facility for RNA sequencing

Thus, all patients on the protocol will have prior to the neoadjuvant cetuximab, an incisional/core biopsy from the primary site and a skin punch biopsy (from the neck or upper trunk), though they already have a diagnosis of SCC. Incisional biopsy is favored over other types (core biopsy) for this biopsy because incisional biopsy has the best chance of supplying an adequate tumor sample. The primary site is favored over a neck lymph node as the biopsy site, as an incisional or core biopsy runs some small risk of seeding the skin of the neck.

After neoadjuvant cetuximab, an additional bx will be obtained from the primary site- because this tissue will only be used for RNA sequencing (and not sent to FoundationOne™ (or other certified genomic analysis facility) for DNA analysis), a core biopsy may be employed here instead of incisional biopsy. A skin punch skin biopsy will also be performed after neoadjuvant cetuximab, preferably from a similar location as the first skin biopsy ie obtain two skin biopsies of neck and neck or right upper chest and right upper chest. If there is a locoregional/distant recurrence or persistence, a third incisional biopsy of locoregional/distant disease is possible, and again paraffin-embedded sample will be sent to FoundationOne™ (or other certified genomic analysis facility) for analysis, and fresh tissue may be obtained for RNA sequencing.

Note that these supplemental biopsies (excluding the biopsy establishing a diagnosis of SCC) are highly encouraged, but are not absolutely necessary for participation in the protocol.

11.3 Collection and Handling Procedures at Rutgers New Jersey Medical School

[figure not shown]
- a. OHRS will coordinate with otolaryngology regarding the date and time of pending biopsies. These biopsies will consist of pre-cetuximab primary site tumor and skin biopsies, followed on a later date, by post-cetuximab primary site tumor and skin biopsies. The procedures for obtaining, processing, and transporting these specimens are identical for pre and post-cetuximab biopsies. Note that these biopsies are for research purposes only, as the patient must already have pathologically proven SCC in order to qualify for this protocol, and that these additional biopsies do not in any way determine how the patient will be treated. Accordingly, these additional biopsies will not pass through Rutgers New Jersey Medical School- Newark pathology, but instead will be stored and transported to Rutgers CINJ BRS.
- b. Otolaryngology
 - a. (Drs [name], [name] or designate) will obtain incisional/core biopsy from the primary site. In order to biopsy for this protocol, the primary site must be accessible without the need for endoscopy, anesthesia or operating room ie these will mostly be oropharyngeal primaries. Ideal size of the tumor specimen is 0.5 cm x 0.5 cm (though it is recognized that this may not be possible for most specimens, and there will be some degree of trial and error for the first few patients in terms of adequate tissue for RNA sequencing).
 - b. ENT will also obtain a skin punch biopsy from the neck, shoulders or upper chest. If the above biopsy from the primary site is not obtainable, the skin biopsy will still be obtained.
- c. Transport from otolaryngology to storage
 - a. OHRS ([name] or designate) will keep specimens moist and cool, with wet paper towel and ice over specimens to minimize RNA degradation while transporting, and then will place specimens in a cryo-vial with RNAlater. Before immersion in RNAlater, cut large tissue samples to ≤0.5 cm in any single dimension, and then place the fresh tissue in 5–10 volumes of RNAlater. The cryo-vial should be labeled with the study patient sequence number, date received, and the words “Pre (or Post)-drug tumor bx in RNAlater” and placed in 4°C refrigerator in a designated lab in the Cancer Building.
- d. Transportation from designated lab in Cancer Building to CINJ BRS
 - a. On the same day or the day after biopsies are taken, the PI, [name] or [name] will take the above tissue samples from the designated lab in the Cancer Building and deliver to CINJ BRS. Primary tumor samples and skin samples will be transported in an approved container with wet ice. Every effort will be made to transport within 1-2 days, but 3 days will be allowed in exceptional situations.
- e. Handling of tissues at Rutgers CINJ BRS
 - a. The primary tissue specimen will be split into two pieces. One part of the primary tissue specimen will be placed in a cryo-vial with **RNAlater**. Before immersion in RNAlater, cut large tissue samples to ≤0.5 cm in any single dimension, and then place the fresh tissue in 5–10 volumes of RNAlater. The cryo-vial should be labeled with the study patient sequence number, date

[figure not shown]
received, and the words “Pre (or Post)-drug tumor bx in RNAlater” and placed in 4°C refrigerator. When ready to freeze, these biopsies will have the supernatant removed and be placed into -80 freezer for storage.

Periodically, these frozen tissues will be delivered to Genomic Facility ([name] or designate) by the BRS.

- b. Another part of the primary tissue specimen will be put into **formalin** with the study patient sequence number, date received, and the words “Pre (or Post)-drug tumor bx in formalin.” This specimen will subsequently be made into a paraffin block. The paraffin block containing Pre-drug tumor biopsies will be verified to have SCC by a qualified pathologist and then sent to FoundationOne™ (or other certified genomic analysis facility) once funds are available. The paraffin block containing Post-drug tumor will be verified to have SCC by a qualified pathologist and stored for IHC.
 - i. In case the paraffin block is found to not contain SCC, then the corresponding tumor sample in RNAlater may be examined for SCC. If no SCC is found in either sample, then none of these samples will be sent to the CINJ Genomic Facility or to FoundationOne™. Repeat tumor biopsies will not be performed in this case. However, if the pre-cetuximab tumor sample is devoid of SCC, the post-cetuximab tumor biopsy will still be obtained and processed.
 - ii. If no research tumor biopsies are performed (beyond that required for diagnosis) or all research tumor biopsies are devoid of SCC, Rutgers NJMS pathology will supply the tumor specimen in paraffin block used for diagnosis for possible analysis by FoundationOne™.
- c. The cryo-vial with skin biopsy should be labeled with the study patient sequence number, date received, and the words “Pre (or Post)-drug skin biopsy” and placed in 4°C refrigerator. When ready for freezing, these biopsies will have the supernatant removed and be placed into -80 freezer for storage. Periodically, these frozen tissues will be delivered to Genomic Facility ([name] or designate) by the BRS.

Rutgers New Jersey Medical School - Newark BIOPSY FLOWCHART (Applicable for both pre and post cetuximab tissue samples)

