1. Analyze the relationship of known DNA mutations in tumor per the FoundationOne™ (or other certified genomic analysis facility) genomic profile, and correlate to clinical endpoints such as locoregional control.
2. Analyze any changes in protein production at the tumor in response to 3 weeks of cetuximab i.e., does the tumor attempt to bypass the effect of EGFR inhibitor by a) accelerating protein production downstream of EGFR receptor or b) transferring dependence to a completely different pathway from EGFR such as IGF-1R?
3. Analyze any changes in protein production at the skin in response to 3 weeks of cetuximab? Are there markers in the skin that might indicate susceptibility to develop folliculitis during cetuximab? Or do they shed light on the strong relationship between folliculitis and efficacy of cetuximab?

Molecular investigations include: 1) Genomic testing of tumor DNA using the FoundationOne™ (or other certified genomic analysis facility) genomic profile from paraffin embedded tumor samples taken before cetuximab or after locoregional/distant failure 2) RNA sequencing of tumor and skin samples from before and after cetuximab, 3) IHC analysis of EGFR downstream pathways. Of these, the first priority will be genomic testing per the FoundationOne assay, as this will be funded by the Cancer Institute of New Jersey Precision Medicine. As funds from grants or the radiation oncology department become available, the other molecular investigations may be completed.

These secondary molecular endpoints are observational, as there is very minimal data available regarding any of these questions. The study will not be powered for these molecular endpoints.

1.2.3 Image correlates: In the current protocol, the role of CT or PET/CT is to provide treatment planning and response assessment during the course of the treatment. All patients will have PET/CT imaging prior to the treatment, and after 3 months of all the treatment. There will also be CT neck with IV contrast after 3 weeks of neoadjuvant cetuximab but prior to radiation therapy. With this full panel of image set, the current protocol would allow for further study to investigate

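### The diagnostic-block fallback in 11.3 misses patients with no usable pre-cetuximab sample but SCC in the post-cetuximab biopsy, leaving them no planned pre-treatment FoundationOne source

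*Combined protocol and SAP*

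**What the plan says.** Section 1.2.2 makes FoundationOne profiling the first priority among the molecular investigations, on paraffin tissue from before cetuximab or after failure. Its first goal is to "Analyze the relationship of known DNA mutations in tumor per the FoundationOne" profile and relate these to endpoints such as locoregional control.

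Section 11.3, item e (handling at the biospecimen repository), sets the routing:

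- Pre-cetuximab block: "The paraffin block containing Pre-drug tumor biopsies will be verified to have SCC by a qualified pathologist and then sent to FoundationOne", once funds allow.
- Post-cetuximab block: "The paraffin block containing Post-drug tumor will be verified to have SCC by a qualified pathologist and stored for IHC". Section 11.2 allows a core biopsy at this time point "because this tissue will only be used for RNA sequencing", and adds that the tissue does not go to FoundationOne.
- Item b.i: if neither the paraffin half nor the RNAlater half of a tumor sample contains SCC, neither is sent and the biopsy is not repeated. However, "if the pre-cetuximab tumor sample is devoid of SCC, the post-cetuximab tumor biopsy will still be obtained and processed".
- Item b.ii, the fallback: "If no research tumor biopsies are performed (beyond that required for diagnosis) or all research tumor biopsies are devoid of SCC", the medical school's pathology department "will supply the tumor specimen in paraffin block used for diagnosis for possible analysis by FoundationOne".

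Section 11.2 describes the supplemental biopsies as encouraged but not required for participation.

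**The concern.** The fallback is meant to rescue the baseline profile when the research biopsies fail. Its trigger, however, looks at all research tumor biopsies together, while only the pre-cetuximab one can feed FoundationOne before radiation. SCC in the post-cetuximab biopsy switches the fallback off although that tissue will not be used for the assay. The diagnostic block is itself pre-cetuximab tissue, so withholding it for this reason serves no stated purpose.

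At stake is a little avoidable loss of data in the first-priority assay. The loss also follows a pattern: among patients without a usable pre-cetuximab sample, those with SCC found after three weeks of cetuximab lose the planned source, and the others keep it. That finding may be related to the outcome with which mutations are to be correlated.

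**Working it through.** The plan states no figure on this point, so there is none to reproduce. The check is a trace of the rules in 11.3 and 11.2, followed by a size estimate under stated assumptions.

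**Trace.** No SCC means none in either half of the sample.

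| Pre-cetuximab research biopsy | Post-cetuximab research biopsy | Planned pre-treatment FoundationOne source |
|---|---|---|
| SCC in the paraffin block | any result, or not done | pre-cetuximab block |
| no SCC | no SCC | diagnostic block |
| no SCC | not done | diagnostic block |
| not done | no SCC | diagnostic block |
| not done | not done | diagnostic block |
| no SCC | SCC | none |
| not done | SCC | none |
| SCC in the RNAlater half only | any result, or not done | none |

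In the sixth and seventh rows the source is lost exactly because the post-cetuximab biopsy was done and contained SCC. The last row is a separate gap. The biopsy is not devoid of SCC, so b.ii is not triggered, while the assay runs on paraffin tissue (11.1). That loss does not depend on the post-cetuximab result.

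**Size of the sixth row.** The only input from the documents is N = 27 (16.2). The four rates are assumptions, each given as low, middle and high:

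- accessible primary with a pre-cetuximab research biopsy: 0.5, 0.6, 0.7
- that sample lacks SCC: 0.1, 0.2, 0.3
- post-cetuximab biopsy done: 0.6, 0.75, 0.9
- SCC in it: 0.5, 0.65, 0.8

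Expected patients without a planned source = 27 × the product of the four rates:

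- low: 27 × 0.5 × 0.1 × 0.6 × 0.5 = 0.4
- middle: 27 × 0.6 × 0.2 × 0.75 × 0.65 = 1.6
- high: 27 × 0.7 × 0.3 × 0.9 × 0.8 = 4.1

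This leaves out the seventh and eighth rows, for which the documents give no basis for a rate.

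**Sensitivity, with every patient biopsied before cetuximab.** Take 16 responders and 27 − 16 = 11 non-responders (16.2). Let q be the chance that the pre-cetuximab sample lacks SCC, and s the chance that the post-cetuximab biopsy is done and contains SCC. Expected loss = 16 × q × s(responders) + 11 × q × s(non-responders):

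- q = 0.1, s = 0.3 and 0.7: 0.48 + 0.77 = 1.25
- q = 0.2, s = 0.3 and 0.7: 0.96 + 1.54 = 2.50, that is 6% of responders and 14% of non-responders
- q = 0.2, s = 0.5 in both: 1.60 + 1.10 = 2.70, that is 10% of each
- q = 0.3, s = 0.5 and 0.9: 2.40 + 2.97 = 5.37

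The second and third lines show that unequal loss between responders and non-responders appears only if s is assumed to differ between them. The documents give no value for s.

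**The case against.** A reader might infer that these patients get no DNA data at all. The documents do not support that:

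- Section 11.2 allows a third biopsy at recurrence or persistence, whose block goes to FoundationOne.
- Section 11.1, item 4, lists DNA sequencing of tumor after as well as before cetuximab, and 11.3.1 describes the DNA extraction and exome sequencing.
- Section 11.3.2 says mutational status can be read from RNA as well as DNA.

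This stands, but none of these routes restores a pre-treatment FoundationOne profile. The third biopsy is optional and makes availability depend on outcome directly. The others are different assays on post-drug tissue and depend on funds. Item 4 of 11.1 also conflicts with the statement in 11.2 that post-cetuximab tissue serves RNA sequencing only.

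A reader might also infer that the loss is governed by tumor persistence and so biases the correlation. That is too strong. The gap arises when a biopsy misses SCC in a proven, untreated tumor or is not done. A post-cetuximab biopsy can miss SCC in the same way and is optional. The protocol judges response by folliculitis and CT, and nothing in it links SCC in a three-week biopsy to locoregional control. A post-treatment finding does enter the rule, but the direction and size of any bias are unknown.

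Item b.ii says when the block will be supplied and does not forbid supply otherwise. That is fair: the case is unaddressed rather than excluded. Staff following the text would still have no instruction to request the block.

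Finally, the stakes are low. The molecular endpoints are observational and unpowered (1.2.2, 16.4). Section 1.2.2 expects institutional funding for FoundationOne, but Section 18 says nothing is in writing. The fallback itself promises only possible analysis. All of this stands and sets the severity.

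**Conclusion.** The gap is real on the plan's own wording. A patient with no usable pre-cetuximab sample and SCC in the post-cetuximab biopsy has no planned pre-treatment FoundationOne source, so availability of the baseline profile depends partly on a post-treatment finding. The RNAlater-only case is a second gap, unrelated to tumor persistence.

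The impact is small: perhaps one or two of 27 patients. This rests entirely on assumed biopsy and detection rates, which could put it anywhere from under one to about five. It concerns one exploratory correlate. The primary endpoint and treatment assignment are unaffected, since 11.3 states that these biopsies do not determine treatment. The documents support neither a total absence of mutation data in these patients nor a demonstrated bias. This is a cheap improvement of low severity.

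**What to change.** Replace the trigger in 11.3, item e, b.ii with: *If no pre-cetuximab research tumor biopsy is performed, or its paraffin block contains no SCC, the diagnostic paraffin block, where one with adequate tissue exists, is supplied for possible FoundationOne analysis, regardless of the post-cetuximab biopsy result.* This closes all three gaps in the trace.

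Also reconcile 11.1, item 4, with 11.2 on whether post-cetuximab tumor is DNA-sequenced.

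The cost is two wording changes and a few more block requests to pathology. No patient has an added procedure. The change recovers nothing for patients diagnosed by FNA only, because 11.2 says FNA tissue is too scant for the molecular work.
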